**Fig 3. Examples of VVFD scenarios to determine clinical outcomes.**

Exploratory outcomes will examine the relationship of microcirculatory function with common clinical biomarkers such as lactate,  $SvO_2$ , venous-to-arterial  $PCO_2$  gap, capillary refill time, and lactate to pyruvate ratio. Markers of endothelial injury and inflammation such as soluble vascular cell adhesion molecule 1 (sVCAM-1), soluble intercellular adhesion molecule 1 (sICAM-1), e-selectin, IL-8, IL-10, and other inflammatory cytokines will be measured. We will also examine mitochondrial complex function in human blood cells, comparing individual complex (I, II, III, and IV) function and reactive oxygen species generation between patients with and without post-operative shock.

### Statistical and analysis plans

Continuous variables characterizing demographical data, microcirculation data, and mitochondrial respiration measurements, and outcomes data will be reported as means with standard deviations if normally distributed or medians with interquartile ranges if not normally distributed. Categorical variables will be represented as frequencies and proportions. To examine the predictive performance of selected variables for the primary outcome, we will construct receiver operator characteristic curves for threshold values of PVD, MHI, lactate,  $SvO_2$ , mean arterial pressure, and cardiac index. A Youden index will be calculated to determine the best cutoff value for determining prolonged VVFDs.

Linear regression modeling will be used to examine the relationship between L/P ratio and postoperative microcirculation variables. We will perform univariate analyses on candidate predictor variables of L/P ratio including PVD, MHI, LFTs, creatinine, CPB time, cross clamp time, and catecholamine administration. Multiple linear regression analysis will be used to model the effect of significant predictors. Repeated measure ANOVA will be used to compare changes in microcirculatory variables, mitochondrial respiration, and mitochondrial reactive oxygen species production over time. To adjust for multiple comparisons, post-hoc pairwise Tukey Kramer t-tests will be performed. All analyses will use statistical software (SAS version 15.1, Cary, NC; Prism v 9.0, Graph-Pad Software, San Diego, CA).

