## **Sample size and power**

Using data from our previous foundational work as well as unpublished pilot data, we anticipate a 1:1 allocation of patients to the high ( $PVD > 22\text{mm/mm}^2$ ) and low group ( $PVD \leq 22\text{ mm/mm}^2$ ). We will need a sample size of at least 134 subjects to detect at least a 2-day difference in ventilator and vasopressor-free days (VVFDs) with a  $\beta=0.8$ , using a one-sided t-test  $\alpha=0.05$  [5,6]. We will enroll a total of 140 subjects to allow for a 5% loss to follow-up (surgical delay, ICU delay, cancelled surgery, etc.) and exclusion due inadequate microcirculation video quality (S1 Appendix).

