### Outcome measures

Our hypothesis is that patients with poor post-operative sublingual functional capillary density (defined as a PVD < 22 mm/mm^2 and MHI > 0.4) will have a higher degree of postoperative cardiovascular and pulmonary organ injury compared to patients with normal postoperative microcirculation. The primary outcome for this study will be VVFDs during the first 30 days after surgery. This outcome was chosen because our elective cardiac surgery patients are managed using early recovery after surgery (ERAS) protocols, with a goal to be extubated and weaned off vasopressors within 24 hours after surgery [21,22]. VVFDs will be calculated as a reverse count of consecutive days without requiring ICU-level respiratory or vasopressor support (**Error! Reference source not found.**). Our research group has used a similar primary outcome in a previous clinical trial [23]. The day of operation (day zero) will not be included as all patients undergoing cardiovascular surgery with CPB require mechanical ventilation and vasoactive medications on the day of surgery. Ventilator days will include mechanical ventilation via endotracheal tube or tracheostomy, high-flow nasal cannula  $\geq$  40 liters/minute with an FiO2 > 40%, or non-invasive positive pressure ventilation not prescribed at home. Non-invasive positive pressure ventilation and HFNC will be included as these both require the patient to remain in our ICU. Vasoactives include epinephrine, norepinephrine, vasopressin, phenylephrine, dobutamine, or milrinone at any dose. Subjects in need of respiratory or vasopressor support on day 30, or die before day 30 will be assigned zero VVFDs. If the patient is discharged prior to hospital day 30 a “last status carried forward” approach will be used. Secondary outcomes will include sequential organ failure assessment (SOFA) score on day 1, day 3, diagnosis of acute kidney injury (defined as an increase in serum creatinine  $\geq$  0.3 mg/dL within 2 days), and hospital length of stay.

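### No planned VVFD analysis adjusts for recorded preoperative risk or bypass time, and the t-test that sizes the study is not carried into the analysis plan

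*Combined protocol and SAP*

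**What the plan says.** Study design and setting describes a prospective, observational, single-center cohort. Under Outcome measures, patients with poor postoperative microcirculation "will have a higher degree of postoperative cardiovascular and pulmonary organ injury compared to patients with normal postoperative microcirculation", and "The primary outcome for this study will be VVFDs during the first 30 days after surgery".

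Sample size and power requires 134 subjects "to detect at least a 2-day difference in ventilator and vasopressor-free days (VVFDs", using a one-sided t-test at alpha 0.05. The groups are PVD above 22 and PVD at or below 22 mm/mm², expected to be equal in size. No covariate is mentioned.

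Statistical and analysis plans covers VVFDs in three ways:

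- the general descriptive summary of outcomes data;
- ROC curves for PVD, MHI, lactate, SvO2, mean arterial pressure and cardiac index: "To examine the predictive performance of selected variables for the primary outcome, we will construct receiver operator characteristic curves";
- a cutoff: "A Youden index will be calculated to determine the best cutoff value for determining prolonged VVFDs".

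Regression is kept for another variable: "Linear regression modeling will be used to examine the relationship between L/P ratio and postoperative microcirculation variables". Candidate predictors, including bypass and cross clamp time, are screened one at a time, and then "Multiple linear regression analysis will be used to model the effect of significant predictors". The L/P ratio is in the exploratory list: "Exploratory outcomes will examine the relationship of microcirculatory function with common clinical biomarkers such as lactate" and, later in the same sentence, the L/P ratio.

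Demographic and resuscitation data lists STS score, euroSCORE II, bypass time and cross clamp time among the recorded variables. The two risk scores enter no planned model, and the two times enter only as L/P predictors.

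**The concern.** PVD groups are formed by observation, not by randomization. Patients with higher preoperative risk or longer bypass may have both lower PVD and longer support. If so, part of any VVFD gap between PVD groups reflects risk that was known before the postoperative image was taken.

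The t-test implied by the sample size and the listed ROC curves would both absorb that risk into the apparent association with PVD. Neither can separate what PVD adds from what STS score and bypass time already told the clinician. The exploratory L/P ratio would get a multivariable model, and the primary outcome would not.

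The t-test also appears only as a sizing assumption. The analysis section does not repeat it, so the form in which the group difference will be reported is left open.

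**Working it through.** **1. Where each element appears**

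| Element | Sample size and power | Statistical and analysis plans |
|---|---|---|
| VVFD comparison between PVD groups | yes, one-sided t-test | not restated |
| VVFD model with STS score, euroSCORE II or bypass time | no | no |
| ROC curves and Youden cutoff for VVFDs | no | yes |
| Multivariable regression | no | L/P ratio only |

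No other section supplies an adjusted VVFD analysis.

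**2. The plan's own figure**

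Inputs from Sample size and power: difference 2 days, one-sided alpha 0.05, power 0.80 (printed as β = 0.8), 134 subjects split 67/67. No SD is given, so 134 cannot be checked independently. The noncentral t-test reaches 80% power at these inputs when SD = 4.63 days, a standardized difference of 2/4.63 = 0.43. The SD below is this back-solved value.

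**3. Precision of the unadjusted difference**

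- SE = 4.63 × √(2/67) = 0.80 days.
- 90% CI half-width = 1.656 × 0.80 = 1.33 days. This matches the one-sided 0.05 test.
- 95% CI half-width = 1.978 × 0.80 = 1.58 days. Judged by this interval, power for 2 days is about 70% rather than 80%.

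**4. Gap that one recorded risk factor could produce (illustration)**

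Assume a risk factor with correlation r to both continuous PVD and VVFDs, no PVD association once the factor is known, approximate normality and a median split. Then gap = 2√(2/π) × r² × SD = 1.596 × r² × 4.63.

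| r (assumed) | Gap, days | Share of 2 days | Chance the one-sided t-test is significant |
|---|---|---|---|
| 0.2 | 0.30 | 15% | 10% |
| 0.3 | 0.67 | 33% | 21% |
| 0.4 | 1.18 | 59% | 43% |

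The documents give no correlations. The 0.4 row is an upper illustration, because an elective cohort that excludes emergent procedures may have a narrow risk range. If r is read as the correlation with PVD group rather than with continuous PVD, the gap is 2r² × SD, or 0.37, 0.83 and 1.48 days.

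**5. Precision of an adjusted difference**

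SE² = SD²(1 − R²) × 4 / [134 × (1 − 2R²/π)], where R² is the share of variance explained in both PVD and VVFDs.

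- One covariate, r = 0.3 (R² = 0.09): SE = √[21.45 × 0.91 × 4 / (134 × 0.943)] = 0.79, and 95% half-width 1.56 days. With r = 0.2 it is 1.57.
- Two mutually uncorrelated covariates, r = 0.3 each (R² = 0.18): 1.52 days.
- Two covariates correlated 0.4 with PVD but not with VVFDs: 1.77 days.

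**The case against.** The strongest reply is that adjustment is not what the study asks for. Study objective and the abstract's Methods and analysis compare microcirculation with traditional biomarkers and hemodynamic targets, not with STS score or bypass time. An unadjusted difference is a valid marginal association, and the documents claim no effect independent of risk. This stands as far as it goes. The gaps in step 4 are real differences due to risk. A reader might call them false positives, but they are not type I error for the unadjusted comparison. What remains is that the planned analyses cannot show what PVD adds to risk already recorded.

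A reader might also infer that the between-group hypothesis has no planned estimate at all. The documents do not support that. Sample size and power names the groups, outcome, test and alpha, so the t-test is fairly read as the intended comparison. The ROC curves also estimate an association between PVD and VVFD status. Failure to restate the t-test is missing detail, and the lack of any adjusted analysis is the weightier part. Sample size and power also cites an S1 Appendix that is not in the supplied text and may hold more detail.

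A third objection is that a mean difference suits VVFDs poorly. They are bounded near 30 and set to zero for death or for support on day 30. Suppose, as an assumption, that every other patient scored 29. Then SD = 29√[p(1 − p)] = 4.63 at p = 2.6% zeros, about 3 to 4 of 134 patients, and one extra zero in a group of 67 moves its mean by 29/67 = 0.43 days. Robust standard errors do not remove that sensitivity. This objection stands, and the fix answers it with a sensitivity analysis.

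**Conclusion.** The point holds. The sized comparison is not carried into the analysis section, and no section plans a VVFD analysis adjusted for preoperative risk or bypass time, although both are recorded before postoperative imaging. It should be fixed before analysis.

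The absence of an adjusted analysis rests on the text alone. Its size does not: the 0.3 to 0.7 days for correlations of 0.2 to 0.3 depends on assumed correlations, the back-solved SD, normality and a median split. A reader might take these figures as evidence that PVD is confounded in this cohort. They show only what could happen.

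**What to change.** In Statistical and analysis plans:

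1. **Carry the sized comparison forward.** Compare VVFDs between PVD groups by the t-test at one-sided alpha 0.05, and report the mean difference with a 90% CI. A 95% CI may be added, with a note that judging by it lowers power (step 3).
2. **Add a supporting adjusted estimate.** Regress VVFDs linearly on PVD group, STS score and bypass time, with robust standard errors, and report the adjusted difference with its CI. Fix the covariates in advance rather than by univariate significance. This stands beside the unadjusted comparison and does not replace it.
3. **Add a sensitivity analysis.** Use a rank-based or ordinal model, such as proportional odds, with the same covariates.
4. **Fix one group definition and one imaging time before analysis.** Sample size and power uses PVD ≤ 22 alone, while Outcome measures uses PVD < 22 with MHI > 0.4. Incident Dark Field Microscopy has three postoperative times. The choice is the sponsor's.
5. **Keep the ROC analysis.** It serves the prediction aim, which the adjusted difference does not answer.

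The cost is a few sentences and a few lines of code, with no new data. The downside is precision, since 134 was not chosen for the adjusted estimate. Its 95% half-width is about 1.5 to 1.6 days, or about 1.8 if the covariates predict PVD but not VVFDs. If the adjusted difference is 2 days, one-sided power is about 81% with one covariate at r = 0.2 to 0.3. If instead 2 days is the unadjusted gap, the adjusted difference is 2 − 0.30 = 1.70 or 2 − 0.67 = 1.33 days, with power 69% or 52%. Residual confounding may remain.

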## **Abstract**

### **Background**

Despite current resuscitation strategies, circulatory shock and organ injury after cardiac surgery occur in 25-40% of patients. Goal-directed resuscitation after cardiac surgery has generated significant interest, but clinical practice to normalize hemodynamic variables including mean arterial pressure, cardiac filling pressures, and cardiac output may not reverse microcirculation abnormalities and do not address cellular dysoxia. Recent advances in technology have made it possible to measure critical components of oxygen delivery and oxygen utilization systems in live human tissues and blood cells. The MicroRESUS study will be the first study to measure microcirculatory and mitochondrial function in patients with circulatory shock and link these findings with clinical outcomes.

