### **Methods and analysis**

This will be a prospective, observational study that includes patients undergoing elective cardiovascular surgery with cardiopulmonary bypass (CPB). Microcirculation will be quantified with sublingual incident dark field videomicroscopy. Mitochondrial respiration will be measured by performing a substrate-uncoupler-inhibitor titration protocol with high resolution respirometry on peripheral blood mononuclear cells at baseline and serial timepoints during resuscitation and at recovery as a possible liquid biomarker. Plasma samples will be preserved for future analysis to examine endothelial injury and other mechanisms of microcirculatory dysfunction. Thirty-day ventilator and vasopressor-free days (VVFDs) will be measured as a primary outcome, along with sequential organ failure assessment scores, and other clinical parameters to determine if changes in microcirculation and mitochondrial respiration are more strongly associated with clinical outcomes compared to traditional resuscitation targets.

This will be the first prospective study to examine both microcirculatory and mitochondrial function in human patients with circulatory shock undergoing cardiac bypass and address a key mechanistic knowledge gap in the cardiovascular literature. The results of this study will direct future research efforts and therapeutic development for patients with shock.

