## Introduction

Despite current resuscitation practices, circulatory shock and perioperative organ injury after cardiac surgery occur in 25-40% of patients [1,2]. Traditionally, causes of shock after cardiovascular surgery with cardiopulmonary bypass are classified by macrocirculatory derangements (e.g. low cardiac output, vasoplegia, hypovolemia) [3]. Interventions to normalize hemodynamic variables, including mean arterial pressure, cardiac filling pressures, and cardiac output restore the large vessel (macrocirculatory) pressure and flow targets but may not reverse underrecognized disruptions in microcirculatory blood flow and oxygen utilization. Current methods to estimate the balance of oxygen delivery ( $DO_2$ ) relative to demand ( $VO_2$ ) include blood gas-derived calculations and the measurement of downstream biomarkers of anaerobic metabolism such as blood lactate. Using these methods, previous literature has concluded that lactic acidosis after cardiac surgery is unlikely related to inadequate oxygen delivery [4]. Unfortunately these inferences fail to consider the presence of regional blood flow derangements caused by pathologic microcirculatory heterogeneity, which are also associated with severity of postoperative lactic acidosis and organ injury [5,6]. To resolve this important clinical discrepancy, a deeper understanding of the determinants of oxygen transport pathways and oxygen utilization during health, shock, and resuscitation are needed.

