## Materials and methods

### Study objective

The primary objective of the MicroRESUS study is to evaluate the microcirculatory and mitochondrial function in patients following elective cardiovascular surgery with cardiopulmonary bypass, to determine if these parameters outperform traditional biomarkers and global hemodynamic measurements to predict clinical outcomes.

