### Physiologic and pharmacologic data

Systemic hemodynamic data, perfusion data, and blood gas measurements will be collected upon ICU admission, then hourly during the first 6 hours of postoperative care. Cardiac output (CO), cardiac index (CI), central venous pressure (CVP), pulmonary artery pressure (PAP), and mixed venous oxygen saturation ( $SvO_2$ ) will be monitored continuously using a pulmonary artery catheter (Edwards Lifesciences LLC, Irvine, CA, USA). Arterial blood pressure will be measured using a standard invasive arterial line. Intraoperative and post-operative administration of blood products, intravenous fluids, vasoactive agents (vasopressor and inotropes), and sedatives will be recorded at each time point.

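### The ROC analysis of ventilator and vasopressor-free days sets PVD and MHI against only four traditional measures, leaving out filling pressures, capillary refill time and PCO2 gap without a stated reason

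*Combined protocol and SAP*

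**What the plan says.** **Objective.** The Study objective section says the parameters are evaluated "to determine if these parameters outperform traditional biomarkers and global hemodynamic measurements to predict clinical outcomes". The abstract (Methods and analysis) puts the same aim as whether changes in them "are more strongly associated with clinical outcomes compared to traditional resuscitation targets". Neither place lists the comparators.

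**Usual hemodynamic goals.** The Introduction states: "Interventions to normalize hemodynamic variables, including mean arterial pressure, cardiac filling pressures, and cardiac output restore the large vessel (macrocirculatory) pressure and flow targets". The abstract's Background names the same three variables.

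**What is recorded.** Physiologic and pharmacologic data lists, among the variables monitored by pulmonary artery catheter, "central venous pressure (CVP), pulmonary artery pressure (PAP", together with cardiac output, cardiac index and SvO2. Under Biological samples, central venous gases are drawn at each microcirculation measurement, and arterial gases every 1-2 hours for the first 6 ICU hours.

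**What is analysed against VVFDs.** Statistical and analysis plans opens the ROC work with "To examine the predictive performance of selected variables for the primary outcome" and then gives the set: "threshold values of PVD, MHI, lactate, $SvO_2$ , mean arterial pressure, and cardiac index". A Youden index follows. The choice of variables is not explained.

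**Where the other markers go.** The exploratory part of Outcome measures relates microcirculatory function to lactate, SvO2, "venous-to-arterial $PCO_2$ gap, capillary refill time, and lactate to pyruvate ratio". It does not relate these markers to VVFDs.

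**The concern.** The objective speaks of a class of measures, and the analysis covers part of that class. A marker outside the ROC set cannot be shown to predict VVFDs as well as PVD or MHI, or better. If PVD had the highest AUC of the six, the supportable statement would be that it did better than lactate, SvO2, MAP and cardiac index. A report that said it outperformed traditional resuscitation targets would go further than the evidence.

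Timing matters too. If a reader later asks about CVP or capillary refill time and these are added once results are known, the choice will look data-driven. Naming them now, or saying now why they are excluded, avoids that.

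**Working it through.** This is a comparison of lists. No formula decides it.

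**Step 1. The plan's own design figure.** Sample size and power gives 134 subjects for a 2-day VVFD difference, one-sided alpha 0.05 and 80% power, with 1:1 PVD groups. The documents available give no SD, so 134 can only be back-solved. By the normal approximation with 67 per group, SD = 2 / ((1.645 + 0.842) × √(2/67)) = 2 / (2.487 × 0.1728) ≈ 4.66 days. This calculation sizes the PVD-group comparison and contains no ROC input, so lengthening the ROC list does not change it.

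**Step 2. Measures named, recorded and analysed.**

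| Measure | Role given in the protocol | Availability | In VVFD ROC set? |
|---|---|---|---|
| MAP | usual hemodynamic goal | arterial line | yes |
| Cardiac output | usual hemodynamic goal | catheter (CO, CI) | yes, as cardiac index |
| Filling pressures | usual hemodynamic goal | catheter (CVP, PAP) | **no** |
| Lactate | shock criterion; exploratory biomarker | named as a serum measure | yes |
| SvO2 | shock criterion; exploratory biomarker | catheter | yes |
| Capillary refill time | shock criterion; exploratory biomarker | implied; Figure 1 not shown | **no** |
| PCO2 gap | exploratory biomarker | derivable from paired gases | **no** |
| Lactate-to-pyruvate ratio | exploratory biomarker; modelled as an outcome | implied | **no** |

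**Step 3. Coverage.**
- ROC set: 6 variables = 2 microcirculatory + 4 traditional.
- Usual hemodynamic goals: 2 of 3 covered.
- Perfusion criteria for shock (Inclusion criteria, item 2): 2 of 3 covered.
- Biomarkers in the exploratory paragraph: 2 of 5 covered.

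**Step 4. Could the missing markers be read alongside PVD and MHI?** CVP is monitored continuously in the ICU, so a value exists at the postoperative imaging times while the catheter is in place. For PCO2 gap, the venous sample is taken at imaging and arterial gases come every 1-2 hours in the first 6 ICU hours, so the gap can be formed near the ICU-arrival and 2-4 hour measurements. By the day-one measurement arterial gases are drawn only as clinically needed. Capillary refill time appears as a shock criterion and an exploratory biomarker, which implies collection, but the schedule in Figure 1 is not available to confirm it.

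**Step 5. Is there a comparison to extend?** The section specifies curves and a Youden cutoff. It specifies no comparison of AUCs, does not define prolonged VVFDs, and does not say at which time point the markers are read.

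**The case against.** The strongest reply is that the plan never promised a complete list. The variables in the Background and Introduction are background and are introduced as examples. The objective names no markers, the statistical section speaks openly of a selection, and both limbs of the objective are represented: two biomarkers (lactate, SvO2) and two hemodynamic measures (MAP, cardiac index). PCO2 gap and capillary refill time have a role, as exploratory correlates.

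Much of this stands. A reader might infer that the plan names MAP, filling pressures and cardiac output as the targets to be outperformed. The documents do not say so. That reading joins the background text to the objective and remains an inference. The omission is a gap in coverage, and four important measures are already present.

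It is also fair that any extended list needs its own logic. PAP and the lactate-to-pyruvate ratio are omitted as well. The ratio is modelled as an outcome in the plan's linear regression, which is a reason to keep it out. PAP has no stated reason either way. And extra Youden cutoffs would add data-driven thresholds, with no multiplicity control stated for the ROC work.

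What the reply does not supply is a reason for leaving out filling pressures, or for using capillary refill time beside lactate and SvO2 to identify shock but not beside them to predict VVFDs. Describing the set as a selection does not narrow an objective stated for the whole class.

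**Conclusion.** The point holds as a minor, cheap improvement. The ROC set omits filling pressures, capillary refill time and PCO2 gap, and this limits what the primary objective can conclude.

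Its numerical size is unknown, because the documents give no AUCs or correlations. A reader might try to size it by the chance that PVD or MHI ranks first in a shorter rather than a longer list. The documents do not support that: it needs equally informative, exchangeable markers, whereas PVD and MHI come from the same videos and SvO2 and cardiac index from the same catheter, and the plan uses no ranking rule.

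A reader might also infer that superiority is formally tested against an incomplete set. It is not formally tested against any comparator, since no AUC comparison is specified. That gap, and the absence of every mitochondrial variable from the ROC set although the objective includes mitochondrial function, are larger than this one.

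Nor does the point weaken the powered comparison of VVFDs by PVD group, which does not use the ROC list. The conclusion assumes that CVP is available at imaging, as continuous ICU monitoring implies, and that capillary refill time is in fact recorded.

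**What to change.** In Statistical and analysis plans:

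1. Add CVP, venous-to-arterial PCO2 gap and capillary refill time to the markers assessed against VVFDs, or state why each is excluded. Give one line on PAP and the lactate-to-pyruvate ratio if they stay out.
2. Name the postoperative imaging time point, and read every marker at that point, the same as for PVD and MHI.
3. Compare AUCs as paired differences (PVD or MHI minus each traditional marker) with confidence intervals, for example by DeLong's method, in subjects with both readings. Report the number in each pair. This requires the definition of prolonged VVFDs that the section now lacks. The added markers need no Youden cutoff.
4. Limit any statement that a microcirculatory marker outperforms traditional measures to the markers actually compared.

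**Cost.** Three more curves, with no additional patients and no change to the 134 or 140. CVP and blood gases are already planned. Capillary refill collection should be confirmed against Figure 1. Some subjects will lack a reading for an added marker, so those pairs will be smaller and their intervals wider. The comparison also becomes less favourable to PVD and MHI.
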